5.2.2.2 Adverse event collection and reporting

AE collection

Upon enrolment into a trial, the subject's baseline condition is assessed (for instance, by documentation of medical history/concomitant diagnoses), and relevant changes from baseline are noted subsequently.

Subjects will be required to report spontaneously any AEs as well as the time of onset, end, and intensity of these events. In addition, each subject will be regularly assessed by the medical staff throughout the clinical trial and whenever the investigator deems necessary. As a minimum, subjects will be questioned for AEs (and concomitant therapies) at the time points indicated in the [Flow Chart](#). Assessment will be made using non-specific questions such as 'How do you feel?'. Specific questions will be asked wherever necessary in order to more precisely describe an AE.

A carefully written record of all AEs shall be kept by the investigator in charge of the trial. Records of AEs shall include data on the time of onset, end time, intensity of the event, and any treatment or action required for the event and its outcome.

The following must be collected and documented on the appropriate CRF(s) by the investigator:

- From signing the informed consent onwards until an individual subject's end of trial:
 - All AEs (serious and non-serious) and all AESIs
 - The only exception to this rule are AEs (serious and non-serious) and AESIs in Phase I trials in healthy volunteers, when subjects discontinue from the trial due to screening failures prior to administration of any trial medication. In these cases, the subjects' data must be collected at trial site but will not be entered in the CRF or trial database and will not be reported in the CTR.
- After the individual subject's end of trial:
 - The investigator does not need to actively monitor the subject for AEs but should only report any occurrence of cancer and related SAEs and related AESIs of which the investigator may become aware of by any means of communication, e.g. phone call. Those AEs should, however, not be reported in the CRF.

Proprietary confidential information © 2019 Boehringer Ingelheim International GmbH or one or more of its affiliated companies

AE reporting to sponsor and timelines

The Investigator must report SAEs, AESIs, and non-serious AEs that are relevant for the reported SAE or AESI, on the BI SAE form via fax immediately (within 24 hours) to the sponsor's unique entry point (country specific contact details will be provided in the ISF). The same timeline applies if follow-up information becomes available. In specific occasions the Investigator could inform the sponsor upfront via telephone. This does not replace the requirement to complete and fax the BI SAE form.

With receipt of any further information to these events a follow-up SAE form has to be provided. For follow-up information, the same rules and timeline apply as for the initial information.

Information required

All (S)AEs, including those persisting after the individual subject's end of trial, must be followed up until they have resolved, have been assessed as 'chronic' or 'stable', or no further information can be obtained.

Pregnancy

In rare cases, pregnancy might occur in a clinical trial. Once a subject has been enrolled in the clinical trial and has taken trial medication, the investigator must report any drug exposure during pregnancy in a trial participant immediately (within 24 hours) by means of Part A of the Pregnancy Monitoring Form to the sponsor's unique entry point.

Similarly, potential drug exposure during pregnancy must be reported if a partner of a male trial participant becomes pregnant. This requires a written consent of the pregnant partner.

The outcome of the pregnancy associated with the drug exposure during pregnancy must be followed up and reported to the sponsor's unique entry point on the Pregnancy Monitoring Form for Clinical Trials (Part B).

The ISF will contain the Pregnancy Monitoring Form for Clinical Trials (Part A and Part B) as well as non-trial specific information and consent for the pregnant partner.

Pregnancy itself is not to be reported as an AE. In the absence of an accompanying SAE and/or AESI, only the Pregnancy Monitoring Form for Clinical Trials and not the SAE form is to be completed. If there is an SAE and/or AESI associated with the pregnancy, an SAE form must be completed in addition.

5.2.3 Assessment of safety laboratory parameters

For the assessment of laboratory parameters, blood and urine samples will be collected by the trial site at the time points indicated in the [Flow Chart](#) after the subjects have fasted for at least 10 h. Overnight fasting is not required at the discretion of the investigator or designee for retests.

The parameters that will be determined are listed in [Tables 5.2.3: 1](#) and [5.2.3: 2](#). Reference ranges will be provided in the ISF, [Section 10](#).

Proprietary confidential information © 2019 Boehringer Ingelheim International GmbH or one or more of its affiliated companies

Table 5.2.3: 1

Routine laboratory tests

Functional lab group	BI test name [comment/abbreviation]
Haematology	Haematocrit Haemoglobin Red Blood Cell count (RBC) Reticulocytes count White Blood Cells count (WBC) Platelet Count Neutrophils; Eosinophils; Basophils; Monocytes; Lymphocytes
Automatic WBC differential (relative and absolute count possible)	
Manual differential WBC (if automatic differential WBC is abnormal)	Neutrophils (stabs), eosinophils, basophils, monocytes, lymphocytes
Coagulation	Activated Partial Thromboplastin Time (aPTT) Prothrombin time: Quick's test and INR (International Normalization Ratio)
Enzymes	AST [Aspartate transaminase] /GOT, SGOT ALT [Alanine transaminase] /GPT, SGPT Alkaline Phosphatase Gamma-Glutamyl Transferase (GGT) Creatine Kinase [CK] Creatine Kinase Isoenzyme MB [CK-MB, only if CK is elevated] Lactate Dehydrogenase (LDH) Serum tryptase ¹ Thyroid Stimulating Hormone (TSH)
Hormones ¹	
Substrates	Glucose (Plasma) Creatinine Bilirubin, Total Bilirubin, Direct Bilirubin, Indirect Protein, Total Protein electrophoresis ¹ Albumin Alpha-1-Globulin Alpha-2-Globulin Beta-Globulin Gamma-Globulin C-Reactive Protein (CRP) Uric Acid Cholesterol, total Triglyceride Sodium Potassium Chloride Calcium Phosphate (as Phosphorus, Inorganic)
Electrolytes	

Proprietary confidential information © 2019 Boehringer Ingelheim International GmbH or one or more of its affiliated companies

Table 5.2.3: 1 **Routine laboratory tests (cont).**

Functional lab group	BI test name [comment/abbreviation]
Urinalysis (Stix)	Urine Nitrite (qual) Urine Protein (qual) Urine Glucose (qual) Urine Ketone (qual) Urobilinogen (qual) Urine Bilirubin (qual) Urine Erythrocytes (qual) Urine WBC/Leucocytes (qual) Urine pH
Urine sediment (microscopic examination if urine analysis abnormal)	Positive findings will be reported (for instance, the presence of sediment bacteria, casts in sediment, squamous epithelial cells, erythrocytes, leukocytes)

¹ Only at screening.

The tests listed in [Table 5.2.3: 2](#) are exclusionary laboratory tests which may be repeated as required. The results will not be entered in the CRF/database and will not be reported in the CTR. Except for pregnancy test and drug screening, it is planned to perform these tests during screening only. Pregnancy testing in women will be performed at screening, prior to treatment, on Day 92, and as part of the end of trial examination. Drug screening will be performed at screening and at admission to the trial site the day prior to treatment.

Table 5.2.3: 2 **Exclusionary laboratory tests**

Functional lab group	Test name
Drug screening (urine)	Amphetamine/MDA Barbiturates Benzodiazepine Cannabis Cocaine Opiates
Infectious serology (blood)	Hepatitis B surface antigen (qual) Hepatitis B core antibody (qual) Hepatitis C antibodies (qual) HIV-1 and HIV-2 antibody (qual)
Pregnancy test (urine)	Beta human chorionic gonadotropin (beta-HCG)

To encourage compliance with alcoholic restrictions, a breath alcohol test (e.g. Dräger Alcotest® 6510 and Alcotest® 510, Belgium) will be performed at screening and on Day -1, and may be repeated at any time during the study at the discretion of an investigator or designee. The results will not be included in the CTR.

In case of a potential systemic allergic reaction, blood samples for determination of serum tryptase will be collected 0.5 h, 2 h, 6 h, and 24 h after onset of the event.

Proprietary confidential information © 2019 Boehringer Ingelheim International GmbH or one or more of its affiliated companies

The laboratory tests listed in [Table 5.2.3: 1](#) and [5.2.3: 2](#) will be performed with the exception of the drug screening and pregnancy tests. These tests will be performed at the trial site using 'Alere Triage TOX Drug Screen' and Alere® -HCG urine, respectively.

Laboratory data will be transmitted electronically from the laboratory to the trial site.

5.2.4 **Electrocardiogram**

Twelve-lead ECGs (I, II, III, aVR, aVL, aVF, V1 - V6) will be recorded using a computerised electrocardiograph (e.g. MAC 5500, GE Healthcare) at the time points given in the [Flow Chart](#).

All ECGs will be recorded for a 10-sec duration after the subjects have rested for at least 5 min in a supine position. The ECG assessment will always precede all other study procedures of the same time point (except blood drawing from an intravenous cannula which is already in place) to avoid impact of sampling on the ECG quality.

Electrode placement will be performed according to the method of Wilson, Goldberger.

All locally printed ECGs will be evaluated by the investigator or a designee. ECGs may be repeated for quality reasons (like alternating current artefacts, muscle movements, electrode dislocation) and the repeated ECG will be used for analysis. Additional (unscheduled) ECGs may be collected by the investigator for safety reasons.

Abnormal findings will be reported as AEs (during the trial) or baseline conditions (at screening) if judged clinically relevant by the investigator. Any ECG abnormalities will be monitored carefully and, if necessary, the subject will be removed from the trial and will receive the appropriate medical treatment.

5.2.5 **Assessment of other safety parameters**

5.2.5.1 **Vital signs**

Systolic and diastolic blood pressures (BP) as well as pulse rate (PR) or heart rate (heart rate is considered to be equal to pulse rate) will be measured by a blood pressure monitor (e.g. Welch Allyn 530TP and 530TO devices) at the times indicated in the [Flow Chart](#), after subjects have rested for at least 5 min in a supine position. All recordings should be made using the same type of blood pressure recording instrument on the same arm if possible.

5.2.5.2 **Medical examinations**

At screening, the medical examination will include demographics including height and body weight, smoking and alcohol history, relevant medical history and concomitant therapy, review of inclusion and exclusion criteria, review of vital signs (BP, PR), 12-lead ECG, laboratory tests (including drug screen and pregnancy test), and a physical examination. The end of trial examination will include review of vital signs, 12-lead ECG, laboratory tests, recording of AEs and concomitant therapy and a physical examination with determination of weight.

5.2.5.3 Local tolerability

Local tolerability will be assessed as specified in the [Flow Chart](#) by the investigator according to 'swelling', 'induration', 'heat', 'redness', 'pain', or 'other findings'.

5.3 OTHER

5.3.1 Pharmacogenomic evaluation

Not applicable.

5.4 APPROPRIATENESS OF MEASUREMENTS

All measurements performed during this trial are standard measurements and will be performed in order to monitor subjects' safety and to determine parameters in an appropriate way. The scheduled measurements will allow monitoring of changes in vital signs, standard laboratory values, and ECG parameters that might occur as a result of administration of trial medication. The safety assessments are standard, are accepted for evaluation of safety and tolerability of an SC administered drug, and are widely used in clinical trials. The pharmacokinetic parameters and measurements outlined in [Section 5.5](#) are generally used assessments of drug exposure.

5.5 DRUG CONCENTRATION MEASUREMENTS AND PHARMACOKINETICS

Date and clock time of drug administration and pharmacokinetic sampling will be recorded in the CRFs.

Exact time points of plasma sampling will be derived from the electronic data capturing system LabPas and documented in the CRFs by the medical personnel or sent as electronic files to the trial data manager. The actual sampling times will be used for determination of pharmacokinetic parameters.

5.5.1 Pharmacokinetic endpoints

5.5.1.1 Primary endpoints

The following primary endpoints will be determined for BI 655130:

- AUC_{0-tz} (area under the concentration-time curve of the analyte in plasma over the time interval from 0 to the last quantifiable data point)
- C_{max} (maximum measured concentration of the analyte in plasma)

5.5.1.2 Secondary endpoint

The following secondary endpoint will be evaluated for BI 655130:

Proprietary confidential information © 2019 Boehringer Ingelheim International GmbH or one or more of its affiliated companies

- $AUC_{0-\infty}$ (area under the concentration-time curve of the analyte in plasma over the time interval from 0 extrapolated to infinity)

5.5.1.3 Further parameters of interest

The following additional endpoints will be evaluated for BI 655130:

Further pharmacokinetic parameters might be calculated as appropriate.

5.5.2 Methods of sample collection

5.5.2.1 Plasma sampling for pharmacokinetic analysis

For quantification of BI 655130 plasma concentrations, approximately _____ of blood will be taken from an antecubital or forearm vein into a K₂-EDTA (dipotassium ethylenediaminetetraacetic acid) anticoagulant blood drawing tube at the times indicated in the [Flow Chart](#) under “Plasma PK”. Blood will be withdrawn by means of either an indwelling venous catheter or by venipuncture with a metal needle.

The K₂-EDTA-anticoagulated blood samples will be mixed gently and placed on ice until centrifugation for about 10 min at about 2000 g to 4000 g and at approximately 4°C. The blood should be centrifuged to produce plasma as soon as possible after collection, but not later than 30 min after withdrawal. Two aliquots of EDTA plasma sample will be obtained in two labelled polypropylene cryotubes. At a minimum, the sample tube labels should list the following information: BI trial number, subject number, visit, PTM, aliquot #1 or #2, plasma, and PK.

The two aliquots should contain approximately _____ of plasma each. The plasma samples will be stored in a freezer at about -70°C or below at the clinical site until shipment to the analytical laboratory.

Proprietary confidential information © 2019 Boehringer Ingelheim International GmbH or one or more of its affiliated companies

The plasma samples may be used for further methodological investigations (e.g. for stability testing), however, only data related to the analyte will be generated by these additional investigations. The study samples will be discarded after completion of the additional investigations but not later than 5 years after the final study report has been signed.

5.5.3 Analytical determinations

5.5.3.1 Analytical determination of BI 655130 plasma concentration

BI 655130 concentrations in plasma will be determined by a validated immunoassay.

6. INVESTIGATIONAL PLAN

6.1 VISIT SCHEDULE

Exact times of measurements outside the permitted time windows will be documented. The acceptable time windows for screening and end of trial examination are given in the [Flow Chart](#).

Study measurements and assessments scheduled to occur 'before' trial medication administration on Day 1 are to be performed and completed within a 3 h-period prior to the trial drug administration.

The acceptable deviation from the scheduled time for vital signs, ECG and safety laboratory will be

- \pm 15 min up to including 12 h
- \pm 30 min from 12h up to including 48 h
- \pm 120 min from 48 h up to Day 8
- \pm 48h from Day 9 up to Day 15
- \pm 72h from >Day 15 up to the last assessments

If scheduled in the [Flow Chart](#) at the same time as a meal, meal will be only provided after completion of the concomitant procedures. Furthermore, if several measurements including venipuncture are scheduled for the same time, vital signs and 12-lead ECG recordings have to be done first and venipuncture should be the last of the measurements due to its inconvenience to the subject and possible influence on physiological parameters.

For planned individual plasma concentration sampling times refer to the [Flow Chart](#). While these nominal times should be adhered to as closely as possible, the actual sampling times will be recorded and used for determination of pharmacokinetic parameter.

If a subject misses an appointment, it will be rescheduled if possible. The relevance of measurements outside the permitted time windows will be assessed no later than at the Report Planning Meeting.

6.2 DETAILS OF TRIAL PROCEDURES AT SELECTED VISITS

6.2.1 Screening period

After having been informed about the trial, all subjects will give their written informed consent in accordance with GCP and local legislation prior to enrolment in the study.

For information regarding laboratory tests (including drug and virus screening), ECG, vital signs, and physical examination, refer to [Sections 5.2.3 to 5.2.5](#).

6.2.2 Treatment period

Study participants will be admitted to the trial site in the evening of Day -1 and kept under close medical surveillance for at least 48 h following drug administration. The subjects will

Proprietary confidential information © 2019 Boehringer Ingelheim International GmbH or one or more of its affiliated companies

then be allowed to leave the trial site after formal assessment and confirmation of their fitness. On all other study days, the study will be performed in an ambulatory fashion.

Details on treatments and procedures of administration are described in [Section 4.1.4](#).

For details on time points and procedures for collection of plasma samples for PK analysis, refer to [Flow Chart](#) and [Section 5.5.2](#).

The safety measurements performed during the treatment period are specified in [Section 5.2](#) of this protocol and in the [Flow Chart](#). For details on time points for all other trial procedures, refer to the [Flow Chart](#). AEs and concomitant therapy will be assessed continuously from screening until the end of trial examination.

6.2.3 End of trial period

For AE assessment, laboratory tests, recording of ECG and vital signs, and physical examination during the end of trial period, see [Sections 5.2.2](#) to [5.2.5](#).

Subjects who discontinue prematurely the study before the end of the planned treatment period (i.e., Day 176 ±3) should undergo the end of trial visit.

All abnormal values (including laboratory parameters) that are judged clinically relevant by the investigator will be monitored using the appropriate tests until a return to a medically acceptable level is achieved. (S)AEs persisting after subject's end of trial must be followed up until they have resolved, have been sufficiently characterised, or no further information can be obtained.

The end of the trial as a whole is defined by the 'last regular visit completed by last subject' or 'end date of the last open AE' or 'date of the last follow-up test' or 'date of an AE has been decided as sufficiently followed-up', whichever is latest.

7. STATISTICAL METHODS AND DETERMINATION OF SAMPLE SIZE

7.1 STATISTICAL DESIGN – MODEL

7.1.1 Objectives

The trial objectives are stated in [Section 2.2](#).

For the purpose of defining reference and test treatments, the following terminology will be used. The reference treatment (R) will refer to dose group 1, test treatment 1 (T1) refers to dose group 2, test treatment 2 (T2) refers to dose group 4 and test treatment 3 (T3) refers to dose group 3.

7.1.2 Endpoints

Relative bioavailability is to be determined on the basis of the primary and secondary pharmacokinetic endpoints (see [Section 5.5.1](#)).

Safety and tolerability will be determined on the basis of the parameters specified in [Section 5.2.1](#).

7.1.3 Model

The statistical model used for the analysis of primary and secondary endpoints will be an ANOVA (analysis of variance) model on the logarithmic scale. This model will include effects accounting for the following sources of variation: 'treatment' and 'matched pair'. For each matched pair in the study a pair number will be assigned for analysis purpose. The resulting variable 'matched pair' will be considered as random effect.

The model is described by the following equation:

$$y_{kjm} = \mu + \tau_k + p_j + e_{ijkm}, \text{ where}$$

y_{kjm} = logarithm of response (endpoint) measured on subject m in pair j receiving treatment k

μ = the overall mean,

τ_k = the kth treatment effect, $k=1,\dots,4$,

p_j = the jth matched pair effect,

e_{ijkm} = the random error associated with the mth subject in sequence i who received treatment k in period j.

Proprietary confidential information © 2019 Boehringer Ingelheim International GmbH or one or more of its affiliated companies

where $p_j \sim N(0, \sigma_B^2)$ i.i.d., $e_{ijk} \sim N(0, \sigma_W^2)$ i.i.d. and p_j, e_{ijk} are independent random variables (note that the indices 'B' and 'W' correspond to 'between' pairs and 'within' pairs variability, respectively).

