3.3 SELECTION OF TRIAL POPULATION

It is planned that 48 healthy male and female subjects (12 in each dose group) will enter the study. They will be recruited from the volunteers' pool of the trial site. Healthy subjects assigned to Dose Groups 2 - 4 will be matched on an individual level for gender and body weight ($\pm 10\%$) to subjects assigned to Dose Group 1 (perumbilical injection).

A log of all subjects enrolled into the trial (i.e. having given informed consent) will be maintained in the ISF at the investigational site irrespective of whether they have been treated with investigational drug or not.

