3.3.5 Replacement of subjects

In case some subjects do not complete the trial, the trial clinical monitor together with the trial pharmacokineticist and the trial statistician are to decide if and how many subjects will be replaced. Replacement of subjects should always be done in mutual agreement with the principal investigator. A replacement subject will be assigned a unique study subject number, and will be assigned to the same treatment and matching criteria as the subject he or she replaces.

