4.1.2 Method of assigning subjects to treatment groups

Prior to the screening visit, subjects will be contacted in writing and informed about the planned visit dates. The subjects willing to participate will be recruited to dose groups according to their temporal availability. As soon as enough subjects have been allocated to Dose Group 1, matching subjects will be allocated to the other dose groups. Therefore, the allocation of subjects to dose groups is not influenced by trial personnel, but only by the subjects' temporal availability. As the study includes healthy subjects from a homogenous population matched for gender and body weight, relevant imbalances between the dose groups are not expected.

The allocation of subjects will be performed prior to the administration of trial medication. Once a subject number has been assigned to a treatment group, it cannot be reassigned to any other treatment group.

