7.3 PLANNED ANALYSES

7.3.1 Primary analyses

The pharmacokinetic endpoints listed in [Section 5.5.1](#) will be calculated according to the BI Standard Operating Procedure (SOP) 'Standards and processes for analyses performed within Clinical Pharmacokinetics/Pharmacodynamics' [[001-MCS-36-472](#)].

Plasma concentration data and parameters of a subject will be included in the statistical pharmacokinetic (PK) analyses if they are not flagged for exclusion due to a protocol violation relevant to the evaluation of PK (to be decided no later than in the Report Planning Meeting) or due to PK non-evaluability (as revealed during data analysis, based on the criteria specified below). Exclusion of a subject's data will be documented in the clinical trial report.

Relevant protocol violations may be:

- Incorrect trial medication taken, that is, the subject received at least one dose of trial medication the subject was not assigned to
- Incorrect dose of trial medication taken
- Use of restricted medications

Plasma concentrations and/or parameters of a subject will be considered as non-evaluable, if for example:

- The subject experiences emesis that occurred at or before 2 times median tmax of the respective treatment (median tmax is to be determined excluding the subjects experiencing emesis)
- A predose concentration is >5% Cmax value of that subject
- Missing samples/concentration data at important phases of PK disposition curve

The following analysis sets will be defined for this trial:

- Treated set (TS):
This subject set includes all subjects from the RS who were documented to have received one dose of study drug. This is the full analysis set population in the sense of ICH-E9
- Pharmacokinetic parameter set (PKS):
This subject set includes all subjects in the TS who provide at least one primary or secondary PK parameter that was not excluded according to the description above. Thus, a subject will be included in the PKS even if he/she contributes only one PK parameter value for one period to the statistical assessment

Point estimates of the ratios of the geometric means (test/reference) for the primary and secondary endpoints (see [Sections 5.5.1.1](#) and [5.5.1.2](#)), and their two-sided 90% confidence intervals (CIs) will be provided.

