7.3.2 Secondary analyses

The same statistical model as stated in [Section 7.1.3](#) will be repeated for the primary and secondary endpoints but with all sources of variation considered as fixed effects.

Additionally, the pharmacokinetic parameters listed in [Section 5.5.1.3](#) will be calculated and analysed descriptively, if feasible.

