## 7.4 PRIMARY ENDPOINT

Analysis of relative bioavailability of the primary endpoints will be performed as defined in Sections 7.1.3 and 7.3.1 of the CTP.

The statistical model for the primary analysis defined in the CTP Section 7.1.3 is an analysis of variance (ANOVA) model on the logarithmic scale. For each matched pair a pair number will be assigned and included in the model as random effect.

The following comparisons will be analysed: T1/R, T2/R and T3/R.

**CTP Section 7.3.1:** *Further comparisons may be investigated if appropriate (e.g. T1 vs. T2 [...] ).*

A sensitivity analysis will be performed with matched pair as fixed effect.

Primary PK endpoints will also be assessed descriptively. The analysis of standard PK parameters is performed according to BI standards ([5](#)) [001-MCS-36-472\_RD-01].

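### Do the 'matched pair' wording and the unstated number for a replacement subject leave the PK model undefined?

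*Protocol*

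**What the plan says.** Protocol 3.3 states that subjects in Dose Groups 2 to 4 "will be matched on an individual level for gender and body weight" (within 10%) to subjects in Dose Group 1. Protocol 4.1.2 makes Group 1 the anchor: "As soon as enough subjects have been allocated to Dose Group 1, matching subjects will be allocated to the other dose groups".

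Protocol 7.1.3 sets out one model for the log-transformed endpoint: an overall mean, a treatment effect with k = 1 to 4, a single block effect p_j, and a residual. Of the block it says: "For each matched pair in the study a pair number will be assigned for analysis purpose". The response is that of subject m in pair j on treatment k, but the residual is glossed as "the random error associated with the mth subject in sequence i who received treatment k in period j".

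The block is random in the primary fit. Protocol 7.3.2 repeats the model "but with all sources of variation considered as fixed effects". SAP 7.4 keeps the same vocabulary, "For each matched pair a pair number will be assigned and included in the model as random effect", and adds the fixed-effect version as a sensitivity analysis.

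Under Protocol 3.3.5 a replacement gets a new subject number and "will be assigned to the same treatment and matching criteria as the subject he or she replaces". Protocol 7.3.1 defines the PK set: "This subject set includes all subjects in the TS who provide at least one primary or secondary PK parameter that was not excluded".

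**The concern.** Taken literally, a pair is one test subject and one reference subject. With three test groups there would be 36 such pairs, and every Group 1 subject would belong to three of them, which a single block number per subject cannot express. Neither document defines the block in so many words. SAP section 4 corrects another slip in the Protocol (the reference to a randomised set) but leaves this one.

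A replacement's block number is not mentioned either. A replacement given a new number would form a block of one record. Such a block adds nothing to any test/reference contrast when blocks are fixed, and less than it should when blocks are random and the within-set correlation is above zero. Because the PK set keeps any treated subject with one usable parameter, a dropout and the replacement could both supply a Cmax, which raises the question of whether both belong in the block.

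The sequence and period wording looks as if it came from a crossover template, and j then has two meanings. If these gaps allowed materially different codings, the primary ratios and their 90% intervals would depend on a programmer's choice made in an open-label trial.

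**Working it through.** **Inputs.** 48 subjects, 12 per group, gCV about 30%, two-sided 90% interval (Protocol 7.3.1 and 7.6). Four treatment levels and one p_j per subject (Protocol 7.1.3). The documents give no within-set correlation rho, so values from 0 to 0.6 are assumed.

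**1. The plan's own precision figure.** Table 7.6:1 is for two parallel arms of 12, hence 22 df:

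precision = exp[ t(0.95, df) × sigma × sqrt(2/12) × sqrt(chi2(0.95, df)/df) ], with sigma = sqrt(ln(1 + gCV²)).

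At gCV 30%: sigma = sqrt(ln 1.09) = 0.2936, t = 1.717, chi2 = 33.92. This gives exp(1.717 × 0.2936 × 0.4082 × 1.2418) = 1.291, and 100/1.2912 and 100 × 1.2912 give limits of 77.45 and 129.12, as printed. The gCV 25% and 35% rows also reproduce (1.239 and 1.344). The table ignores matching, so the definition of the block cannot affect it.

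**2. Which blocks fit the equation.** Each subject has one j. Each Group 1 subject has one match in each of three groups, and there are 12 Group 1 subjects. That gives 12 blocks of four.

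- Parameters: 1 mean + 3 treatment + 11 block = 15. Residual df = 48 − 15 = 33. All three test/reference contrasts are estimable.
- With 36 numbers and one record per subject, the design matrix has rank 37, and two of the three planned ratios cannot be estimated in the fixed-effect fit. That coding is incompatible with Protocol 7.3.2 and SAP 7.4, so it is not a live alternative.

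**3. Validity on the set-of-four reading.** Simulated 90% interval coverage for T1/R (1,500 runs per value, rho = 0, 0.25, 0.5) is 90.3 to 90.9% with blocks fixed and 90.2 to 90.5% with blocks random. With three members missing from three different sets it is 90.1 to 90.5% and 90.3 to 90.6%. A separate run of the random-effect fit (3,000 runs per value, rho 0 to 0.6) gives 89.5 to 90.0%.

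Precision at gCV 30% with 33 df, multiplying sigma by sqrt(1 − rho), is 1.275, 1.234 and 1.188 at rho = 0, 0.25 and 0.5. The planned 1.29 is slightly conservative.

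**4. Replacements.** Protocol 3.3.5 gives the replacement the same treatment and matching criteria, which is the same slot in the same set. Protocol 7.1.3 numbers matched groups of subjects, and a lone replacement is not one, so nothing in the text creates a block of one.

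As a bound, suppose one Group 1 replacement were miscoded that way. With blocks fixed, the reference is then informed by 11 sets only:

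- Var(mean of tests − R) = (1 + 1/3)/11 = 0.1212
- Var(T1 − mean of tests) = (2/3)/12 = 0.0556
- Sum 0.1768, against 2/12 = 0.1667 when complete. SE ratio = sqrt(1.0606) = 1.030.

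In the random-effect fit, generalised least squares gives SE ratios of 1.000, 1.011 and 1.016 at rho = 0, 0.3 and 0.5.

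**5. Dropout and replacement both contributing.** The PK set definition retains both, and the subject index m allows two subjects in one cell. For Group 1 the set then has five members: 49 records, 34 residual df, SE ratio 0.981 to 0.983 in the random-effect fit and 0.984 in the fixed-effect fit. The interval narrows slightly.

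**6. The residual.** The response carries k, j and m only. Removing the sequence and period wording leaves the same model terms and the same fit.

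**The case for a change.** The best case for acting is that the trial is open-label throughout, including while the analysis is prepared, so the grouping should be settled in writing and not left to inference. The matching criteria are sex and weight within 10%, which several sets could satisfy, so sharing the criteria is not strictly the same as inheriting a set number. Replacement is foreseen, and missing PK data are realistic: the PK table for trial 1368.3 covers 11 + 12 + 11 = 34 of 36 subjects. The remedy would be a few words in SAP 7.4.

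The description of the text stands: 'pair' is loose, the replacement's number is not stated in what can be read, and the sequence and period wording is left over. What does not follow is that the analysis is open. A replacement is recruited for one named subject's place, so the set is known when the replacement is enrolled and before any concentration is measured. The 34 of 36 figure shows missing PK data, not replacement, and Protocol 3.3.5 leaves it to the trial team whether to replace anyone. The SAP contents list also skips some section numbers (5.3, 6.4 and 9), so a convention in withheld text cannot be excluded.

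**Conclusion.** No change to the plan is called for. The wording is clerical, and the missing detail is one that the analysts would fill in the only workable way: 12 sets of four, with a replacement carrying the set number of the subject replaced. On that basis both planned fits are valid, coverage is about 90%, and neither the sample size nor Table 7.6:1 changes.

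The residual risk is small. A single miscoded Group 1 replacement would cost 3.0% in standard error in the sensitivity fit and at most 1.6% in the primary fit at rho up to 0.5, against a planned precision factor of 1.29. Protocol 7.2 sets no acceptance range and tests no hypothesis, so no decision rule turns on a difference of that size.

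This rests on the assumed correlations, on gCV near 30% for the simulated coverage and the precision figures, and on the text that can be read. If either document is revised for another reason, writing 'matched set' and dropping sequence and period from the residual would be a harmless tidy-up.
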